### 3. STUDY DESIGN

This study evaluates the safety, PK, and PD of AT-752 will enroll approximately 60 subjects that meet the inclusion/exclusion criteria. Following screening and informed consent, eligible subjects will be randomized to receive either AT-752 or matching placebo orally TID for 5 days in Cohort 1 of the study. Subsequent cohorts will receive AT-752/placebo either BID or TID, as described in [Figure 3-1](#). Randomization will be stratified by geographic region. Standard-of-care treatment, including acetaminophen, will be permitted during the study.

A schematic of the study design is provided in [Figure 3-1](#).

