In addition, temperature readings will be performed at least 4 times daily, in the morning, mid-day, late afternoon, and evening (approximately every 4 hours while the subject is awake) through the end of treatment. Temperature will be measured orally and will be recorded in a patient diary (and given to the site coordinator for entry in the eCRF).
- d. Hematology/ chemistry/ coagulation to include complete blood count (CBC) including white blood cell (WBC) count with differential count, red blood cell (RBC) count, platelet count, hemoglobin, hematocrit, and RBC indices; aspartate transaminase (AST), alanine aminotransferase (ALT), total and direct bilirubin, alkaline phosphatase, blood urea nitrogen (BUN), creatinine, serum creatine kinase, lipase, bicarbonate or total carbon dioxide, sodium, potassium, chloride, glucose, total protein, albumin, phosphate, calcium, and amylase; international normalized ratio (INR), prothrombin time, and partial thromboplastin time. Urinalysis will be performed with microscopy at indicated visits but treatment with study drug may begin before the screening results have been obtained unless medically required to establish eligibility (at investigator's discretion). Additional urinalysis may be performed as clinically indicated.  
One-time retests of individual screening laboratory parameters or assessments may be permitted in certain scenarios. Such scenarios may include lab processing error, results inconsistent with subject's historical values/medical history, or other extenuating circumstances such as a recent or intercurrent illness potentially affecting screening laboratory results. Standard of care laboratory results prior to informed consent are accepted if performed within 24 hours of screening.
- e. SARS-CoV-2 rapid test performed at screening and Day 6. RIDT performed only at screening.
- f. A dipstick pregnancy test is required at screening. Additional pregnancy tests may be performed locally as clinically indicated.
- g. Rapid point of care (POC) test for DENV NS1 antigen. See [Section 3.1.4](#) for details about assay timing.

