## 5.6 PRIOR AND CONCOMITANT MEDICATIONS

Information regarding prior medications taken by the subject within the 30 days before signing the informed consent form (ICF) as well as concomitant medications taken after starting study drug will be recorded in the subject's eCRF. Any concomitant medication deemed necessary for the welfare of the subject during the study may be given at the discretion of the investigator. This includes standard-of-care treatments/therapies for dengue should subjects deteriorate on-study due to their dengue infection. If a prohibited

concomitant medication is taken, a joint decision will be made by the investigator and the sponsor to continue or discontinue the subject from the study based on the time the medication was administered, its pharmacology and PK, and whether the use of the medication will compromise the safety of the subject or the interpretation of the data. The investigator is responsible for ensuring that details regarding the medication are adequately recorded in the eCRF. Prior and concomitant medications and therapies will be coded using the latest version of the World Health Organization Drug Dictionary.

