# **7. Treatments and Medications**

## **7.1 Prior and Concomitant Medications**

Medications that stop prior to the first dose of study drug will be classified as prior medication. Medications that start on or after the first dose of study drug will be classified as concomitant. If a

medication starts before the first dose of study drug and stops on or after the first dose of study drug, then the medication will be classified as both prior and concomitant.

All prior and concomitant medications will be coded according to the World Health Organization Drug Dictionary (version to be delineated in the CSR) and presented in a data listing.

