Intermediate missing log 10-transformed viral loads (between baseline and the last day) will be linearly interpolated using the last and next available viral loads for AUC calculation for both AUCD5 and AUCD28. Subjects with intermediate missing values will be included in AUC analysis.

Time to viral load (as measured by DENV RNA and viral titre) or NS1 clearance, defined as time to first of 2 consecutive results of undetectable viral load or NS1, will be described using Kaplan-Meier methods. The median time to viral clearance and the estimated proportions of patients with viral clearance will be summarized by treatment group. Patients who do not receive a record of a negative test result by RT-PCR/viral titre or NS1 antigen assay by the last observation timepoint will be treated as censored at the final scheduled evaluation time point.

Subgroup analysis by DENV serotype will be carried out for the following endpoints: change of DENV viral load (as measured by DENV RNA and viral titre) from baseline, viral load AUC, time to viral load or NS1 clearance. Descriptive statistics (N, mean, standard deviation, median, minimum and maximum, and 95% CI) will be presented by treatment group.

Number and percentage of subjects with treatment-emergent amino acid substitutions in DENV NS5 gene will be compared between the treatment groups (chi-squared test).

Duration of fever is the sum of fever episode durations where fever episode duration is defined as the time from first fever measurement (either at baseline or following a period without fever) to the next measurement without fever. If the last episode has not resolved, duration for that episode will be

censored at the time of the last temperature measurement. Treatments will be compared by log-rank test.

Exploratory biomarkers may include plasma concentrations of cytokines (for example, TNF- $\alpha$ , IFN- $\gamma$ , IL-2, IL-4, IL-5, IL-6, IL-10, IL-12, IL-13, IL-1 $\beta$ , IP-10 and MCP-1). Data will be presented in descriptive statistics by treatment.

Exploratory analyses may be performed to evaluate exposure-response relationship. The relationship between the exposure of AT-752 (AT-281 and its metabolites AT-551, AT-229, and AT-273) and DENV viral load may be explored using graphical displays. Scatter plots of drug exposure versus change in DENC viral load will be provided.

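### Fever duration ends an episode at one afebrile reading and takes no account of permitted acetaminophen, so suppressed readings remove real fever time and no planned table would show unequal use

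*SAP*

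**What the plan says.** Protocol section 8.3.4 leaves the fever method to the SAP. SAP section 12 gives it: "Duration of fever is the sum of fever episode durations", and an episode is "defined as the time from first fever measurement (either at baseline or following a period without fever) to the next measurement without fever". An unresolved last episode is censored at the last temperature. Then: "Treatments will be compared by log-rank test". No minimum afebrile period is required and antipyretics are not mentioned.

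Protocol section 3 states: "Standard-of-care treatment, including acetaminophen, will be permitted during the study". Section 5.6 adds: "Any concomitant medication deemed necessary for the welfare of the subject during the study may be given at the discretion of the investigator". The visible text sets no limit on acetaminophen and no timing of temperature readings relative to it.

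On measurement, Table 3-1 footnote c says "temperature readings will be performed at least 4 times daily, in the morning, mid-day, late afternoon, and evening", about every 4 hours while awake, until the end of treatment.

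Concomitant medications go into the eCRF (Protocol 5.6). SAP section 7.1 codes them and puts them in a listing; it plans no summary table. Fever is an exploratory endpoint (SAP 3.2.3), and SAP section 4 calls all confidence intervals and p-values descriptive.

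**The concern.** Fever is the one outcome here that a permitted non-study drug suppresses directly. A reading taken while acetaminophen is acting ends the episode, and the clock restarts only at the next febrile reading. The measured duration then depends on antipyretic intake as well as on the illness.

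The same SAP section is stricter elsewhere: clearance of viral load and of NS1 needs two consecutive negative results. Fever has no confirmation rule. The endpoint is also named as either the time until fever resolves or how long it lasts, but section 12 defines only the summed duration.

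Antipyretic use comes after randomisation and follows symptoms, which treatment may change. If it differs between arms, the log-rank comparison cannot separate that difference from a drug effect, and no planned table would alert the reader. The sample-size section says results will be interpreted on all the data together, and fever is part of that.

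**Working it through.** The plan states no effect size, variance or power for fever, so there is no figure of its own to reproduce. Its power figures concern viral load and do not bear on this point.

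**Within one patient.** From the plan: at least four readings a day, about 4 h apart while awake; an episode ends at the next afebrile reading; episodes are summed. Assumed: clock times of 08, 12, 16 and 20 h, and a continuous true fever of 72 h from 08 h on Day 1 to 08 h on Day 4, so that the 08 h reading on Day 4 is afebrile.

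Duration = sum over episodes of (first afebrile reading after the start − start of episode).

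| Readings suppressed each day | Sum | Duration | Change from 72 h |
|---|---|---|---|
| None | 72 | 72 h | 0% |
| 12 h | 4 + 20 + 20 + 16 | 60 h | −17% |
| 20 h | 12 + 12 + 12 | 36 h | −50% |
| 12 h and 20 h | 3 × (4 + 4) | 24 h | −67% |

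Cross-check: a suppressed reading costs the time to the next febrile reading. At 12 h that is 4 h; at 20 h it is 12 h, because nothing is read overnight. Over three days: 72 − 3×4 = 60; 72 − 3×12 = 36; 72 − 3×(4 + 12) = 24.

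**Between arms.** The documents give no inputs for this, so every input below is assumed. Two arms of 15; four readings a day, 4 h apart, for 6 days; first reading febrile; true fever with mean 72 h and SD 24 h (values held within 8 to 130 h). Each later febrile reading is masked independently with the stated probability. Log-rank test at two-sided 0.05, with 1,500 simulated trials per row. A true benefit of 24 h means a mean of 48 h on active drug.

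| True benefit | Masked, placebo / active | Measured benefit | Log-rank rejects |
|---|---|---|---|
| 0 h | 0 / 0% | 0.0 h | 5.7% |
| 0 h | 25 / 25% | 0.2 h | 5.9% |
| 0 h | 50 / 50% | 0.0 h | 6.8% |
| 24 h | 0 / 0% | 23.6 h | 69% |
| 24 h | 25 / 25% | 17.7 h | 60% |
| 24 h | 50 / 50% | 11.8 h | 46% |
| 0 h | 40 / 20% | −14.4 h | 49% |
| 24 h | 50 / 25% | −0.3 h | 7% |

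Equal masking produces no material false difference but shrinks a real one. Unequal masking can manufacture a difference (here in favour of placebo; swapping the arms would reverse the sign) or cancel a true benefit.

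**The case against.** **What stands.** Summing episodes is already better than stopping at the first afebrile reading, because fever that returns when an antipyretic wears off is counted; only the masked interval is lost. Fever duration under usual care, acetaminophen included, is a legitimate treatment-policy quantity. The fair criticism is that the SAP does not say this is what it estimates. The trial is randomised and double-blind, so equal use is a reasonable expectation within a cohort, although placebo is pooled over three sequential cohorts and practice could drift between them. Listings are sorted by treatment, so with about 60 patients a gross imbalance could be found by hand.

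**Stronger readings that the documents do not support.**

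- A reader might infer from Protocol 5.6, which records drugs taken "within the 30 days before signing the informed consent form (ICF) as well as concomitant medications taken after starting study drug", that an antipyretic taken between consent and first dose goes unrecorded. Table 3-1 schedules concomitant medications at Screening and on Day 1, section 3.1.1 requires them to be recorded before the initial dose, and SAP 7.1 classes any drug stopped before first dose as prior. This is loose wording, not a gap in capture.
- A reader might infer that headache would drive more acetaminophen use on active drug. Protocol 1.2.1 lists headache among the commonest events across the Phase 1 study, but reports only gastrointestinal events as more common on AT-752 than on placebo.
- A reader might take the 17% to 67% reductions as the bias of the comparison. They assume that the same clock reading is masked every day in one patient, and they say nothing about a difference between arms.

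**Conclusion.** The concern holds as a minor to moderate weakness of an exploratory analysis. By its own wording, the fever rule lets one suppressed reading delete real fever time: 4 h for a noon reading and 12 h for an evening reading under the assumed clock times, and up to 48 of 72 h in the most extreme pattern shown. With similar use in both arms, the consequence is mainly dilution. A false or hidden difference needs unequal use. The documents give neither a rate nor a direction for that, so the simulated sizes show only what could happen. What the plan lacks is a statement of how antipyretic use is handled, a confirmed-resolution analysis, and a table that would let a reader judge whether use differed. The fever comparison is not invalid, and the primary RNA endpoint is unaffected.

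**What to change.** 1. In SAP section 12, add time to sustained resolution: the first afebrile reading after first dose that is followed only by afebrile readings for at least 24 h. Analyse it by Kaplan-Meier and log-rank, alongside the summed duration. State the temperature cut-off, which section 12 does not give.
2. State that the summed duration is measured regardless of antipyretic use.
3. Add a sensitivity analysis in which a reading taken soon after a recorded antipyretic does not count as afebrile. Pre-specify the interval and apply it where intake times are available; the documents do not say whether clock times are recorded. This belongs in a sensitivity analysis only. As the main definition, it would prevent a patient taking acetaminophen for pain from resolving, and so would build antipyretic use into the endpoint.
4. In SAP section 7.1, add a by-arm table of antipyretic use: percentage of patients and, where recorded, doses per day.

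The cost is SAP wording, two added analyses and one table. The real downside is censoring: diary temperatures stop at the end of treatment, so patients whose fever settles late cannot show 24 h of afebrile readings. Keeping the summed duration beside the new endpoint limits that loss. Permitted care does not change.

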### 13. Interim Analysis

No formal interim analysis was planned in the study. As this is an early phase study, the Sponsor may perform unblinded interim reviews of the data during the course of the study.

### 14. Changes in the Planned Analysis

There are no changes to the planned analyses described in the protocol.

### 15. References

#### Schedule of Events

Assessment	Screening	Treatment Period			Follow-up					
		Day 1	Days 2-4	Day 5	Day 6	Day 7	Day 8	Day 14±1	Day 28±3/ EOS (Early Termination)	
Visit Type	Site	Site	Site or Mobile	Site or Mobile	Site	Site or Mobile	Site or Mobile	Site or Mobile	Site	
Eligibility criteria	X									
Informed consent a	X									
Demographics	X									
Medical history	X									
Concomitant medications	X	X	X	X	X	X	X	X	X	
Physical examination b	X	X	X	X	X	X	X	X	X	
Vital signs c	X	X	X	X	X					

12-lead ECG (triplicate-consecutive)	X				X				X
Chemistry/ hematology/coagulation d	X	X	Day 2, 4		X		X	X	X
Urinalysis w/ microscopy d	X	X			X		X		
SARS-CoV-2 rapid test, RIDT e	X				X				
Pregnancy testing f	X								
NS1 rapid test g	X								
Pharmacokinetic assessments h		X	Day 2 and Day 3 or 4						
DENV serotype testing i	X								
Viral load j	X	X	X	X	X	X	X	X	X (Day 28 only)
NS1 antigen test	X	X	X	X	X	X	X	X	X (Day 28 only)
Plasma Biomarker	X	X	Day 2, 4		X		X	X	X (Day 28 only)
Adverse events k	X	X	X	X	X	X	X	X	X
Randomization	Prior to dosing								
Study drug administration		X	X	X					
Accountability of returned drug, and review of patient diary					X				X (Early Termination only)

---

Abbreviations: DENV = dengue virus; ECG = electrocardiogram; ELISA = enzyme-linked immunosorbent assay; NS1 = nonstructural protein 1; RIDT = rapid influenza diagnostic test

Informed consent will be performed before any study procedures are conducted. Results from standard of care evaluations that are available prior to informed consent are accepted if performed within 24 hours of screening. A full physical examination, including height and weight, will be performed at screening and Day 28, except height will not be collected at Day 28. Symptom-directed physical examinations will be performed at the remaining visits.

On Day 1, vital signs should be collected pre-administration of study drug. Vital sign measurements should be performed before any scheduled blood collections. On subsequent days (Days 2-6), vital signs can be collected at any time.

In addition, temperature readings will be performed at least 4 times daily, in the morning, mid-day, late afternoon, and evening (approximately every 4 hours while the subject is awake) through the end of treatment. Temperature will be measured orally and will be recorded in a patient diary (and given to the site coordinator for entry in the eCRF).

Hematology/ chemistry/ coagulation to include complete blood count (CBC) including white blood cell (WBC) count with differential count, red blood cell (RBC) count, platelet count, hemoglobin, hematocrit, and RBC indices; aspartate transaminase (AST), alanine aminotransferase (ALT), total and direct bilirubin, alkaline phosphatase, blood urea nitrogen (BUN), creatinine, serum creatine kinase, lipase, bicarbonate or total carbon dioxide, sodium, potassium, chloride, glucose, total protein, albumin, phosphate, calcium, and amylase; international normalized ratio (INR), prothrombin time, and partial thromboplastin time. Urinalysis will be performed with microscopy at indicated visits but treatment with study drug may begin before the screening results have been obtained unless medically required to establish eligibility (at investigator's discretion). Additional urinalysis may be performed as clinically indicated.

One-time retests of individual screening laboratory parameters or assessments may be permitted in certain scenarios. Such scenarios may include lab processing error, results inconsistent with subject's historical values/medical history, or other extenuating circumstances such as a recent or intercurrent illness potentially affecting screening laboratory results. Standard of care laboratory results prior to informed consent are accepted if performed within 24 hours of screening.

SARS-CoV-2 rapid test performed at screening and Day 6. RIDT performed only at screening.

A dipstick pregnancy test is required at screening. Additional pregnancy tests may be performed locally as clinically indicated.

Rapid point of care (POC) test for DENV NS1 antigen. See Protocol [Section 3.1.4](#) for details about assay timing. Pharmacokinetic (PK) plasma samples will be collected on Day 1 at time 0 (pre-dose; before the first dose on Day 1) and 24 hours after Dose 1. For TID dosing, samples will be obtained before Dose 7 and 0.5, 1, 2, 4, and 6 hours after Dose 7. This serial PK sampling for TID dosing may be done for Dose 7, 8, or 9, based on site/patient convenience. For BID dosing, samples will be obtained before Dose 5 and 0.5, 1, 2, 4, 6, and 8 hours after Dose 5. This serial PK sampling for BID dosing may be done for Dose 5, 6, or 7, based on site/patient convenience. For blood samples, a  $\pm$  10-minute window for time points  $\leq$  4 hours;  $\pm$  15 minute for time points between 4 and 24 hours. PK samples will also be obtained at any early study discontinuation visits. The timing of these PK samples relative to the last 2 (most recent) doses will be recorded. See Protocol [Section 3.1.4](#).

Subjects can begin treatment with study drug before the DENV-serotype results are obtained.

Measurement of plasma viremia by viral titre and using a serotype-specific, real-time reverse transcription polymerase chain reaction (RT-PCR) assay. Subjects can begin treatment before the viral load results are obtained. See Protocol [Section 3.1.4](#) for details about the timing of this assay.

Adverse events are collected beginning at screening. Treatment-emergent adverse events and serious adverse events will be assessed from the time of study drug dosing until end of study and should be followed until they are resolved, stable, or judged by the investigator to be not clinically significant.

After subjects are confirmed eligible at screening, randomization and the initial dosing should occur within 24 hours, the initial dose should be given on the same day as screening, if possible. TID dosing at screening/Day 1 can begin in the morning, at mid-day, or in the evening (see Protocol [Section 3.1.2](#)). BID dosing on Screening/Day 1 can begin in the morning or the evening (See Protocol [Section 3.1.3](#)).

Note that if the initial dose of study drug is administered on the same day as screening (at mid-day or in the evening), the last dose(s) of study drug will be administered on Day 6.

---

